| 132 | 60 | 26.7 | 25.8 | 25.0 | 24.2 | 23.4 | 22.7 | 22.0 | 21.3 | 20.7 | 20.1 | 19.5 | 19.0 | 18.4 | 17.9 | 17.5 | 17.0 | 16.5 | 16.1 | 15.7 | 15.3 | 14.9 | |
| 134 | 61 | 27.2 | 26.3 | 25.4 | 24.6 | 23.8 | 23.1 | 22.4 | 21.7 | 21.1 | 20.4 | 19.9 | 19.3 | 18.8 | 18.2 | 17.7 | 17.3 | 16.8 | 16.4 | 15.9 | 15.5 | 15.1 | |
| 137 | 62 | 27.6 | 26.7 | 25.8 | 25.0 | 24.2 | 23.5 | 22.7 | 22.1 | 21.4 | 20.8 | 20.2 | 19.6 | 19.1 | 18.5 | 18.0 | 17.5 | 17.1 | 16.6 | 16.2 | 15.8 | 15.4 | |
| 139 | 63 | 28.1 | 27.1 | 26.2 | 25.4 | 24.6 | 23.8 | 23.1 | 22.4 | 21.8 | 21.1 | 20.5 | 19.9 | 19.4 | 18.8 | 18.3 | 17.8 | 17.4 | 16.9 | 16.5 | 16.1 | 15.6 | |
| 141 | 64 | 28.5 | 27.6 | 26.7 | 25.8 | 25.0 | 24.2 | 23.5 | 22.8 | 22.1 | 21.5 | 20.8 | 20.2 | 19.7 | 19.1 | 18.6 | 18.1 | 17.6 | 17.2 | 16.7 | 16.3 | 15.9 | |
| 143 | 65 | 28.9 | 28.0 | 27.1 | 26.2 | 25.4 | 24.6 | 23.8 | 23.1 | 22.4 | 21.8 | 21.2 | 20.6 | 20.0 | 19.4 | 18.9 | 18.4 | 17.9 | 17.4 | 17.0 | 16.6 | 16.1 | |
| 146 | 66 | 29.4 | 28.4 | 27.5 | 26.6 | 25.8 | 25.0 | 24.2 | 23.5 | 22.8 | 22.1 | 21.5 | 20.9 | 20.3 | 19.7 | 19.2 | 18.7 | 18.2 | 17.7 | 17.3 | 16.8 | 16.4 | |
| 148 | 67 | 29.8 | 28.8 | 27.9 | 27.0 | 26.2 | 25.4 | 24.6 | 23.8 | 23.1 | 22.5 | 21.8 | 21.2 | 20.6 | 20.0 | 19.5 | 19.0 | 18.5 | 18.0 | 17.5 | 17.1 | 16.6 | |
| 150 | 68 | 30.3 | 29.3 | 28.3 | 27.4 | 26.6 | 25.7 | 24.9 | 24.2 | 23.5 | 22.8 | 22.1 | 21.5 | 20.9 | 20.3 | 19.8 | 19.2 | 18.7 | 18.2 | 17.8 | 17.3 | 16.9 | |
| 152 | 69 | 30.7 | 29.7 | 28.7 | 27.8 | 26.9 | 26.1 | 25.3 | 24.6 | 23.8 | 23.1 | 22.5 | 21.8 | 21.2 | 20.6 | 20.1 | 19.5 | 19.0 | 18.5 | 18.0 | 17.6 | 17.1 | |
| 154 | 70 | 31.2 | 30.1 | 29.2 | 28.2 | 27.3 | 26.5 | 25.7 | 24.9 | 24.2 | 23.5 | 22.8 | 22.1 | 21.5 | 20.9 | 20.4 | 19.8 | 19.3 | 18.8 | 18.3 | 17.8 | 17.4 | |
| 157 | 71 | 31.6 | 30.6 | 29.6 | 28.6 | 27.7 | 26.9 | 26.0 | 25.3 | 24.5 | 23.8 | 23.1 | 22.5 | 21.8 | 21.2 | 20.7 | 20.1 | 19.6 | 19.1 | 18.6 | 18.1 | 17.6 | |
| 159 | 72 | 32.1 | 31.0 | 30.0 | 29.0 | 28.1 | 27.2 | 26.4 | 25.6 | 24.9 | 24.1 | 23.4 | 22.8 | 22.1 | 21.5 | 20.9 | 20.4 | 19.8 | 19.3 | 18.8 | 18.3 | 17.9 | |
| 161 | 73 | 32.5 | 31.4 | 30.4 | 29.4 | 28.5 | 27.6 | 26.8 | 26.0 | 25.2 | 24.5 | 23.8 | 23.1 | 22.4 | 21.8 | 21.2 | 20.7 | 20.1 | 19.6 | 19.1 | 18.6 | 18.1 | |
| 163 | 74 | 33.0 | 31.9 | 30.8 | 29.8 | 28.9 | 28.0 | 27.1 | 26.3 | 25.6 | 24.8 | 24.1 | 23.4 | 22.8 | 22.1 | 21.5 | 20.9 | 20.4 | 19.9 | 19.3 | 18.9 | 18.4 | |
| 165 | 75 | 33.4 | 32.3 | 31.2 | 30.2 | 29.3 | 28.4 | 27.5 | 26.7 | 25.9 | 25.1 | 24.4 | 23.7 | 23.1 | 22.4 | 21.8 | 21.2 | 20.7 | 20.1 | 19.6 | 19.1 | 18.6 | |
| 168 | 76 | 33.8 | 32.7 | 31.7 | 30.6 | 29.7 | 28.8 | 27.9 | 27.0 | 26.2 | 25.5 | 24.7 | 24.0 | 23.4 | 22.7 | 22.1 | 21.5 | 20.9 | 20.4 | 19.9 | 19.4 | 18.9 | |
| 170 | 77 | 34.3 | 33.2 | 32.1 | 31.0 | 30.1 | 29.1 | 28.2 | 27.4 | 26.6 | 25.8 | 25.1 | 24.4 | 23.7 | 23.0 | 22.4 | 21.8 | 21.2 | 20.7 | 20.1 | 19.6 | 19.1 | |
| 172 | 78 | 34.7 | 33.6 | 32.5 | 31.5 | 30.5 | 29.5 | 28.6 | 27.8 | 26.9 | 26.1 | 25.4 | 24.7 | 24.0 | 23.3 | 22.7 | 22.1 | 21.5 | 20.9 | 20.4 | 19.9 | 19.4 | |
| 174 | 79 | 35.2 | 34.0 | 32.9 | 31.9 | 30.9 | 29.9 | 29.0 | 28.1 | 27.3 | 26.5 | 25.7 | 25.0 | 24.3 | 23.6 | 23.0 | 22.4 | 21.8 | 21.2 | 20.7 | 20.1 | 19.6 | |
| 176 | 80 | 35.6 | 34.4 | 33.3 | 32.3 | 31.2 | 30.3 | 29.3 | 28.5 | 27.6 | 26.8 | 26.0 | 25.3 | 24.6 | 23.9 | 23.3 | 22.6 | 22.0 | 21.5 | 20.9 | 20.4 | 19.9 | |
| 179 | 81 | 36.1 | 34.9 | 33.7 | 32.7 | 31.6 | 30.7 | 29.7 | 28.8 | 28.0 | 27.2 | 26.4 | 25.6 | 24.9 | 24.2 | 23.6 | 22.9 | 22.3 | 21.7 | 21.2 | 20.6 | 20.1 | |
| 181 | 82 | 36.5 | 35.3 | 34.2 | 33.1 | 32.0 | 31.0 | 30.1 | 29.2 | 28.3 | 27.5 | 26.7 | 25.9 | 25.2 | 24.5 | 23.9 | 23.2 | 22.6 | 22.0 | 21.4 | 20.9 | 20.4 | |
| 183 | 83 | 37.0 | 35.7 | 34.6 | 33.5 | 32.4 | 31.4 | 30.4 | 29.5 | 28.7 | 27.8 | 27.0 | 26.3 | 25.5 | 24.8 | 24.1 | 23.5 | 22.9 | 22.3 | 21.7 | 21.1 | 20.6 | |
| 185 | 84 | 37.4 | 36.2 | 35.0 | 33.9 | 32.8 | 31.8 | 30.8 | 29.9 | 29.0 | 28.2 | 27.3 | 26.6 | 25.8 | 25.1 | 24.4 | 23.8 | 23.1 | 22.5 | 22.0 | 21.4 | 20.9 | |
| 187 | 85 | 37.8 | 36.6 | 35.4 | 34.3 | 33.2 | 32.2 | 31.2 | 30.2 | 29.3 | 28.5 | 27.7 | 26.9 | 26.1 | 25.4 | 24.7 | 24.1 | 23.4 | 22.8 | 22.2 | 21.7 | 21.1 | |
| 190 | 86 | 38.3 | 37.0 | 35.8 | 34.7 | 33.6 | 32.5 | 31.6 | 30.6 | 29.7 | 28.8 | 28.0 | 27.2 | 26.4 | 25.7 | 25.0 | 24.3 | 23.7 | 23.1 | 22.5 | 21.9 | 21.4 | |
| 192 | 87 | 38.7 | 37.5 | 36.2 | 35.1 | 34.0 | 32.9 | 31.9 | 31.0 | 30.0 | 29.2 | 28.3 | 27.5 | 26.8 | 26.0 | 25.3 | 24.6 | 24.0 | 23.3 | 22.7 | 22.2 | 21.6 | |
| 194 | 88 | 39.2 | 37.9 | 36.7 | 35.5 | 34.4 | 33.3 | 32.3 | 31.3 | 30.4 | 29.5 | 28.6 | 27.8 | 27.1 | 26.3 | 25.6 | 24.9 | 24.2 | 23.6 | 23.0 | 22.4 | 21.9 | |
| 196 | 89 | 39.6 | 38.3 | 37.1 | 35.9 | 34.8 | 33.7 | 32.7 | 31.7 | 30.7 | 29.8 | 29.0 | 28.2 | 27.4 | 26.6 | 25.9 | 25.2 | 24.5 | 23.9 | 23.3 | 22.7 | 22.1 | |
| 198 | 90 | 40.1 | 38.8 | 37.5 | 36.3 | 35.1 | 34.1 | 33.0 | 32.0 | 31.1 | 30.2 | 29.3 | 28.5 | 27.7 | 26.9 | 26.2 | 25.5 | 24.8 | 24.2 | 23.5 | 22.9 | 22.4 | |
| 201 | 91 | 40.5 | 39.2 | 37.9 | 36.7 | 35.5 | 34.4 | 33.4 | 32.4 | 31.4 | 30.5 | 29.6 | 28.8 | 28.0 | 27.2 | 26.5 | 25.8 | 25.1 | 24.4 | 23.8 | 23.2 | 22.6 | |
| 203 | 92 | 41.0 | 39.6 | 38.3 | 37.1 | 35.9 | 34.8 | 33.8 | 32.7 | 31.8 | 30.8 | 30.0 | 29.1 | 28.3 | 27.5 | 26.8 | 26.0 | 25.4 | 24.7 | 24.1 | 23.4 | 22.8 | |
| 205 | 93 | 41.4 | 40.0 | 38.7 | 37.5 | 36.3 | 35.2 | 34.1 | 33.1 | 32.1 | 31.2 | 30.3 | 29.4 | 28.6 | 27.8 | 27.1 | 26.3 | 25.6 | 25.0 | 24.3 | 23.7 | 23.1 | |
| 207 | 94 | 41.9 | 40.5 | 39.2 | 37.9 | 36.7 | 35.6 | 34.5 | 33.4 | 32.5 | 31.5 | 30.6 | 29.7 | 28.9 | 28.1 | 27.3 | 26.6 | 25.9 | 25.2 | 24.6 | 23.9 | 23.3 | |
| 209 | 95 | 42.3 | 40.9 | 39.6 | 38.3 | 37.1 | 35.9 | 34.9 | 33.8 | 32.8 | 31.8 | 30.9 | 30.1 | 29.2 | 28.4 | 27.6 | 26.9 | 26.2 | 25.5 | 24.8 | 24.2 | 23.6 | |

22. APPENDIX III. CLINICAL LABORATORY TESTS

The following clinical laboratory tests are to be performed.

Clinical Safety Panel

HEMATOLOGY: (Differential reported as % and absolute value)

Hemoglobin, Hematocrit, Platelet Count, RBC Count, WBC - Total Count, WBC Differential, (Basophils, Eosinophils, Lymphocytes, Monocytes, Neutrophils)

BLOOD CHEMISTRIES: Alanine aminotransferase (ALT), Alkaline Phosphatase (ALP), Aspartate aminotransferase (AST), Bicarbonate (HCO₃), Bilirubin (Total, Direct, Indirect), Blood Urea Nitrogen (BUN), Calcium (Ca), Chloride (Cl), Creatinine, Glucose, Magnesium (Mg), Phosphorus (P), Potassium (K), Protein (Total), Sodium (Na), Uric Acid, Albumin

URINALYSIS: Blood, Glucose, Ketones, Leukocyte esterase, Microscopic examination, Nitrites, pH, Protein

THYROID PANEL: Thyroid stimulating hormone (TSH)

URINE DRUG SCREENING: Amphetamines, Barbiturates, Benzodiazepines, Cannabinoids, Cocaine, Cotinine, Methamphetamines, Methadone, Methylenedioxymethamphetamine (MDMA), Phencyclidine (PCP), Opiates, Oxycodone

OTHER TESTS: Serum Pregnancy (β -HcG) (in female subjects only ≥ 8 years of age), Urine Pregnancy Test (in female subjects only ≥ 8 years of age)

Laboratory reports will be initialed and dated on all pages by the Investigator listed on the Form FDA 1572 (MD or DO). Laboratory test results will be reviewed by the Investigator as they become available. The Investigator must determine the clinical significance of all out-of-range lab values (except drug screens). Possibly drug-related or clinically relevant abnormal values of uncertain causality must be repeated. Any abnormal values that persist should be followed at the discretion of the Investigator.

23. APPENDIX IV. CLINICALLY RELEVANT CYP2B6 SUBSTRATES OR INDUCERS OR INHIBITORS (GENERIC NAMES)

The following drugs are prohibited during this study.

| Substrate | Inhibitor | Inducer |
|------------------|--------------|---------------|
| artemisinin | clopidogrel | artemisinin |
| bupropion | thiotapec | carbamazepine |
| cyclophosphamide | ticlopidine | efavirenz |
| efavirenz | voriconazole | nevirapine |
| ifosfamide | | phenobarbital |
| ketamine | | phenytoin |
| meperidine | | rifampin |
| methadone | | |
| nevirapine | | |
| propofol | | |
| selegiline | | |
| sorafenib | | |

Flockhart DA. Drug Interactions: Cytochrome P450 Drug Interaction Table. Indiana University School of Medicine (2007). <http://medicine.iupui.edu/clinpharm/ddis/table.aspx>. Accessed 4 March 2016.

24. APPENDIX V. WORSENING OF ADHD-RS-IV HV TOTAL SCORE NECESSARY FOLLOWING WASHOUT FROM PRIOR METHYLPHENIDATE TREATMENT

On Day -1 a subject must demonstrate evidence of worsening of ADHD symptoms following a minimum 72-hour washout from prior methylphenidate treatment. Worsening in ADHD symptoms is defined as meeting both of the following criteria:

- ADHD-RS-IV HV total score ≥ 26
- At least a 30% worsening in ADHD-RS-IV HV total score since the last assessment.

Table 8 provides a list of screening ADHD-RS-IV HV total scores and associated scores that indicate a 30% worsening following the minimum 72-hour washout from prior methylphenidate treatment.

Table 8: 30% Worsening in ADHD RS-IV HV Total Score

| ADHD-RS-IV HV Total Score at Day -7 | 30% Worsening in ADHD RS-IV HV Total Score at Day -1 |
|-------------------------------------|--|
| 20 | ≥ 26 |
| 21 | ≥ 28 |
| 22 | ≥ 29 |
| 23 | ≥ 30 |
| 24 | ≥ 32 |
| 25 | ≥ 33 |
| 26 | ≥ 34 |
| 27 | ≥ 36 |
| 28 | ≥ 37 |
| 29 | ≥ 38 |
| 30 | ≥ 39 |
| 31 | ≥ 41 |
| 32 | ≥ 42 |
| 33 | ≥ 43 |
| 34 | ≥ 45 |
| 35 | ≥ 46 |
| 36 | ≥ 47 |

Table 8: 30% Worsening in ADHD RS-IV HV Total Score (Continued)

| ADHD-RS-IV HV Total Score at Day -7 | 30% Worsening in ADHD RS-IV HV Total Score at Day -1 |
|--|---|
| 37 | ≥ 49 |
| 38 | ≥ 50 |
| 39 | ≥ 51 |
| 40 | ≥ 52 |
| 41 | 54 |

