Subjects will be confirmed to have been treated with a methylphenidate for at least 6 weeks prior to Day -7. Subjects will be evaluated by the investigator and confirmed to demonstrate adequate clinical response to prior treatment with methylphenidate based on clinical assessment and informant interview, as well as, review of available medical records. On Day -7 the ADHD Rating Scale Version IV - Home Version (modified for investigator administration) (ADHD-RS-IV HV) will be completed and subjects will attend a half-day practice laboratory classroom session intended to familiarize them with classroom schedules and procedures related to SKAMP evaluations, PERMP tests, and other planned activities. All subjects will discontinue prior methylphenidate treatment for 3 - 5 days prior to Day -1 in order to ensure that there is at least a 72-hour washout from methylphenidate prior to the assessment of ADHD symptoms on Day -1. The day before randomization, the subject's parent/legal guardian will be contacted by study site staff in order to confirm clinical worsening of the subject's ADHD symptoms since discontinuation of methylphenidate. Clinical worsening is defined as an ADHD-RS-IV HV total score ≥ 26 and demonstration of at least a 30% worsening in ADHD-RS-IV HV total score (see [Section 24](#), Appendix V) since the last assessment and following the minimum 72-hour washout

from prior methylphenidate treatment. Subjects who do not demonstrate clinical worsening following washout of methylphenidate will be considered screen failures and not randomized.

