8.1. Subject Inclusion Criteria

The subjects who fulfill the following criteria will be included in the study.

1. Subject is 6 - 12 years old, inclusive at screening and randomization.
2. At least one of the subject's parents/legal guardians must give written informed consent, including privacy authorization, prior to study participation. The subject will provide informed assent prior to study participation.
3. Subject meets Diagnostic and Statistical Manual of Mental Disorders Fifth Edition (DSM-5) criteria for a primary diagnosis of ADHD (inattentive, hyperactive, or combined presentation) at screening established by a comprehensive psychiatric evaluation that reviews DSM-5 criteria and confirmed using the Schedule for Affective Disorders and Schizophrenia for School-Age Children-Present and Lifetime version (K-SADS-PL) at screening.
4. Subject is currently on a treatment regimen of a methylphenidate formulation within the approved labeled dose range for ADHD for at least 6 weeks prior to Day -7 with the same dose level for at least 1 week immediately prior to Day -7. Note: If any doses of methylphenidate were missed during the week prior to Day -7, the subject's eligibility will be discussed with the Medical Monitor.
5. In the opinion of the investigator, methylphenidate is well tolerated and clinically effective based on clinical assessment and informant interview, as well as, review of available medical records. Note: The ADHD Rating Scale Version IV - Home Version (modified for investigator administration) (ADHD-RS-IV HV) will be administered at Screening by the investigator to inform clinical evaluation.
6. Subject is male or a non-pregnant, non-lactating female.
7. Subject, if female, must not be pregnant or breastfeeding, and if ≥ 8 years of age must have a negative serum pregnancy test at screening.
8. Female subjects of childbearing potential and male subjects with female partners of childbearing potential must practice true abstinence (consistent with lifestyle) and must agree to remain abstinent or agree to use an effective and medically acceptable form of birth control, from the time of informed consent/assent to at least 14 days after the last dose of the study drug has been taken. See [Section 10.5](#) for information on acceptable methods of birth control.

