10.3.1. Prohibited Medications

Subject must not have taken any of the following medications within the timeframe listed:

- Anticonvulsants for seizure control within 2 years prior to screening
- Antipsychotic medication within 6 months prior to screening
- Herbal or complementary treatments, eg, St. John's Wort, within 7 days prior to Day 1
- Any antidepressant medication (eg, bupropion, SSRI/ SNRI, tricyclic, etc) within 7 days prior to Day 1
- MAO inhibitor within 21 days prior to Day 1
- Amphetamine-based product as treatment for ADHD within 6 weeks prior to the start of screening
- Non-methylphenidate product as treatment for ADHD within 6 weeks prior to the start of screening.

All subjects will discontinue their methylphenidate regimen for 3 - 5 days prior to Day -1 in order to ensure that there is at least a 72-hour washout from methylphenidate prior to the assessment of ADHD symptoms on Day -1. Treatment with any ADHD medication is prohibited during the washout period. In addition, all subjects are required to refrain from other prohibited medications for at least 7 days, unless otherwise specified, prior to the first dose of study drug.

Use of any of the following medications is not permitted during the study from screening through the EOS visit:

- Lithium (any lithium preparation or formulation)
- Alpha-2 adrenergic receptor agonists (including clonidine and guanfacine), modafinil, armodafinil, atomoxetine, or any stimulant class agent (methylphenidate- or amphetamine-based)
- Antidepressant medications (eg, bupropion, SSRI/SNRI, MAO inhibitor, tricyclic, etc)
- Anticonvulsant medications (eg, phenytoin, carbamazepine, lamotrigine, valproic acid, etc) and antipsychotic medications
- Pseudoephedrine-containing medications
- Medications with significant effect on blood pressure or heart rate. Intermittent use of asthma treatments is permitted but should be discussed with the medical monitor.
- Sleep aids with the exception of melatonin
- Diphenhydramine except topical formulations
- Herbal or complementary treatments, eg, St. John's Wort
- CYP2B6 substrates or inhibitors or inducers of CYP2B6 (see [Section 23](#), Appendix IV).

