11.5.1.3. Visit 3 (Day -1): Telephone Contact

The parent/legal guardian of the subject will be contacted by telephone to determine the subject's continued eligibility for the study. The following study-related procedures will be performed:

- Review inclusion/exclusion criteria
- Record prior and concomitant medications
- Administer ADHD-RS-IV HV

If a subject has not demonstrated evidence of worsening of ADHD symptoms as measured by ADHD-RS-IV HV total score ≥ 26 and at least a 30% worsening in ADHD-RS-IV HV total score (see [Section 24](#), Appendix V) since the last assessment and following a minimum 72-hour washout from prior methylphenidate treatment he or she is not eligible to continue in the study.

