11.5.2.2. Visit 5 (Day 15): Second Laboratory Classroom Day

At this visit the subject should arrive at the clinic by 6:30 AM and the following study-related procedures will be performed:

- Perform study drug accountability
- Collect dosing diary
- Record prior and concomitant medications
- Record AEs
- Measure weight, record BMI
- Collect vital signs once. For each subject the time should be the same as on Day 1.
- Administer C-SSRS since last visit version
- Collect samples for UDS, urine pregnancy test for females \geq 8 years of age
- Conduct 7 classroom sessions according to the Laboratory Classroom Manual.

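### The urine drug screen on both classroom days does not list methylphenidate, so abstinence from it on Day 15 rests on medication review alone

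*Protocol*

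**What the plan says.** Inclusion criterion 4 (Protocol 8.1) requires that "Subject is currently on a treatment regimen of a methylphenidate formulation within the approved labeled dose range for ADHD". Criterion 5 adds that the investigator judges it effective and well tolerated.

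The drug is then stopped "in order to ensure that there is at least a 72-hour washout from methylphenidate prior to the assessment of ADHD symptoms on Day -1" (Protocol 7.1). Protocol 10.3.1 bars "any stimulant class agent (methylphenidate- or amphetamine-based" products and runs through the end-of-study visit.

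Four provisions bear on whether children stay off it:

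- **Day -1 (Protocol 11.5.1.3).** "The parent/legal guardian of the subject will be contacted by telephone to determine the subject's continued eligibility for the study". Medications are recorded and the ADHD-RS-IV HV is given. The child must score at least 26 and be at least 30% worse than at the last assessment (exclusion 2).
- **Day 1 and Day 15 (Protocol 11.5.2.1 and 11.5.2.2).** Medications are recorded, and both visit lists include "Collect samples for UDS, urine pregnancy test for females".
- **The panel (Protocol Appendix III).** "URINE DRUG SCREENING: Amphetamines, Barbiturates, Benzodiazepines, Cannabinoids, Cocaine, Cotinine, Methamphetamines, Methadone, Methylenedioxymethamphetamine (MDMA), Phencyclidine (PCP), Opiates, Oxycodone".
- **Storage (Protocol 9.3).** Parents are told to put other ADHD treatments out of the child's reach.

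SAP Section 9 plans no pharmacokinetic sampling. In SAP 4.5, taking a drug prohibited under 10.3.1 is important deviation 3, and a positive urine drug screen at any visit is important deviation 5. Either one removes a child from the per-protocol (PP) population.

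**The concern.** The trial compares dasotraline with placebo in children whose effective drug has been withdrawn. Both classroom days are interpretable only if the child is off methylphenidate. The screen taken on those days looks for drugs such as phencyclidine and oxycodone, but does not list the one prohibited drug that every child was recently taking.

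Day 15 is where this matters. Children on placebo have been without active treatment for two weeks after a documented worsening. If some are given methylphenidate before the second classroom day and this is not reported, their SKAMP scores fall and the treatment difference shrinks. Under the primary analysis (SAP 7.5.1), and under the sensitivity analyses in SAP 7.1.1.2, which deal with missing scores, these children count as ordinary placebo observations. The PP analysis would not remove them either, because nothing identifies them.

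**Working it through.** **1. Panel against prohibited list.** Appendix III names 12 analytes or classes, and none is methylphenidate. No other test in that appendix measures it.

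**2. Could the amphetamine entry cover it?** The documents do not settle assay cross-reactivity, but they suggest the panel is not meant to detect methylphenidate. The same screen is run at Visit 1, when every child should be taking it. If it reacted, nearly every child would screen positive under exclusion 27 and need the exception for prescribed medication. Each would also meet SAP deviation 5, which has no such exception, and the PP population would be close to empty. Section 10.3.1 also names methylphenidate-based and amphetamine-based agents separately, though that concerns prohibited classes and not assays.

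**3. What is checked, and when.**

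| Period | Medication review | Symptom gate | Laboratory test for methylphenidate |
|---|---|---|---|
| Day -1 (washout) | yes | yes, caregiver-informed | none listed |
| Day 1 | yes | no | none listed |
| Day 15 | yes | no | none listed |

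**4. The plan's own power.** Inputs from Protocol 15.1: difference 4.0, SD 5, 50 completers per arm, two-sided 5%. The noncentrality is (4.0/5) × √(50/2) = 0.8 × 5 = 4.0 on 98 degrees of freedom. The exact t-test power is 97.7%, which agrees with the stated 95% or more.

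**5. Illustration of dilution on Day 15.** Two inputs are not in the documents and are assumed: the fraction f of placebo children taking methylphenidate without declaring it, and its effect m on the mean SKAMP-Combined score. Use on dasotraline is set to zero.

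- Difference = 4.0 − f × m.
- Placebo variance for the mixture = 25 + f(1 − f)m². SD for the test = √[(25 + placebo variance)/2].

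For example, with m = 4 and f = 0.10 the difference is 4.0 − 0.4 = 3.6. The placebo variance is 25 + 0.09 × 16 = 26.44, and the SD is √25.72 = 5.07.

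| m | f | Difference | Power, SD held at 5 | Mixture SD | Power, mixture SD |
|---|---|---|---|---|---|
| 4 | 5% | 3.8 | 96.4% | 5.04 | 96.2% |
| 4 | 10% | 3.6 | 94.6% | 5.07 | 94.0% |
| 4 | 20% | 3.2 | 88.7% | 5.13 | 87.1% |
| 8 | 5% | 3.6 | – | 5.15 | 93.3% |
| 8 | 10% | 3.2 | – | 5.28 | 85.1% |
| 8 | 20% | 2.4 | – | 5.49 | 58.1% |

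The m = 4 rows borrow the protocol's assumed dasotraline difference. The m = 8 rows show how strongly the result depends on that choice. The calculation follows the plan's two-sample t-test and takes no credit for covariate adjustment in the ANCOVA.

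**6. Day 1.** The baseline classroom day ends before the first dose, so undeclared use then should not differ by arm. Baseline is also a covariate in the primary model. The main effect would be added noise.

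**The case against.** **Washout is not unchecked.** A reader might infer from the panel that neither washout nor abstinence is verified at all. The documents do not support that for washout. A child still benefiting from methylphenidate would be expected to fail the Day -1 worsening gate, which a qualified site rater scores. The gate rests on caregiver information and comes a day before the classroom, but it is a real check. It has no counterpart on Day 15.

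**Other safeguards exist.** Parents are told to remove other ADHD treatments, and the sample schedule keeps children on site from 6:30 am to 8:45 pm. Deviation 3 already covers methylphenidate. All this stands. However, being on site does not exclude a dose before arrival, the daily calls are dosing reminders, and deviation 3 can act only on use that someone reports.

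**The harm is conjecture.** The documents do not say what families keep at home or that placebo children would be dosed more often, and families are blinded. This also stands: the rate, the effect and the imbalance between arms are all assumed. At 5% use and a 4-unit effect, the loss of power is slight. Use concentrated on placebo can hide an effect but cannot create one.

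**A positive Day 1 result would not prove a missed washout.** Correct. It could reflect a dose after the Day -1 call or, depending on an unstated detection window, drug taken before a compliant washout. Protocol Table 7 records the urine screen through EDC and not the laboratory system, which suggests an on-site kit. Whether a suitable kit exists is not in the documents, and a laboratory result might arrive after randomization. The test should therefore not be used as an automatic eligibility rule.

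**Conclusion.** The point holds as a gap in verification. No laboratory test listed in the plan looks for methylphenidate. On Day 15 that leaves medication review as the only check, deviation 3 dependent on report, and deviation 5 not designed to catch this drug.

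The size is uncertain. Undeclared use at 5% to 20% of placebo children with a 4-unit effect takes power from 97.7% to between about 96% and 87%. A larger methylphenidate effect would cost more. These figures assume a use rate, an effect and use on placebo only, none of which the documents give.

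Two stronger conclusions should not be drawn. The stated power of at least 95% is not wrong, since it reproduces on the plan's own inputs. Nor is the baseline shown to be invalid, since Day 1 use should fall equally on both arms. This is a cheap improvement to the plan and does not correct a stated figure.

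**What to change.** **Protocol Appendix III.** Add methylphenidate or its metabolite to the analytes tested on the Day 15 urine, and on the Day 1 urine, by kit or by laboratory assay on the same sample. Leave the screening sample out, because children are then on the drug by design.

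**SAP 4.5.** State three things:

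- A positive Day 15 result counts as important deviation 3 for the PP analysis.
- A positive Day 1 result is flagged as possible prohibited use. It is adjudicated before unblinding against the assay's detection window and the medication record, and is not taken as proof that the 72-hour washout was missed.
- Methylphenidate results are handled by these rules and not by deviation 5, whose present wording would exclude on any positive screen.

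The change needs no new visit or sample and leaves N, alpha and the primary analysis as they are. It costs a small assay fee, and a few children may leave the PP set.
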